Aim #3: Using LCA, identify novel delirium phenotypes (latent classes) based on psychomotor activity, arousal, severity, etiology, and pathophysiological plasma biomarkers (inflammation, endothelial dysfunction, and BBB injury), and explore if they modify early cognitive intervention's effect on 4-month global cognition. *We hypothesize that we will establish three novel delirium phenotypes using LCA and that one phenotype will benefit more from the early cognitive training and rehabilitation intervention.*

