5.2a. Delirium will be assessed for in the ED at screening and 3-hours, and once daily throughout the hospitalization if enrolled for 10 days and at discharge, whichever comes first. Trained CTAs will perform the **modified Brief Confusion Assessment Method (bCAM, 1 minute, Appendix B)** in non-mechanically ventilated patients or the **Confusion Assessment Method for the Intensive Care Unit (CAM-ICU, Appendix C)**. The modified bCAM can be reliably performed by our non-physician research staff. It is 82% to 86% sensitive and 93 to 96% specific for delirium with a kappa of 0.87 indicating excellent interobserver reliability.⁴³ The CTAs will also perform the **Delirium Assessment Battery (Appendix G, 5 minutes)** to capture additional delirium assessments such as the CAM, 3D-CAM, and 4AT for our sensitivity analyses.⁴⁴⁻⁴⁷

5.2.b. Delirium Heterogeneity Factors

Delirium heterogeneity factors will be collected once daily in the ED and hospital to help identify delirium phenotypes using LCA (Aim #3). These heterogeneity assessments do not require any additional patient interaction and arousal, psychomotor activity, and severity can be observed while performing the delirium assessments. **Arousal** will be determined with the **Richmond Agitation Sedation Scale (RASS, Appendix H)**^{48,49} Patients will be categorized as having delirium with normal arousal (RASS = 0), decreased arousal (RASS < 0) or increased arousal (RASS > 0). **Psychomotor activity** will be assessed by using the **Delirium Motor Subtyping Scale-4 (DMSS-4, Appendix I)**.⁵⁰ This observational scale is an abbreviated version of the more complex 11-item Delirium Motor Subtyping Scale (DMSS) with very good agreement (κ = 0.63 to 0.92).^{50,51} Patients will be categorized into hypoactive, hyperactive, mixed, and no psychomotor subtype delirium. **Delirium severity** will be determined by the short form **Confusion Assessment Method Severity (CAM-S, Appendix J)** and will be categorized as none (0 points), low (1 point), moderate (2 points), or severe (3 to 7 points).⁵²

5.2.c. Establishing Pre-illness Cognition and Intelligence

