5.3. Medical Record Review for Index Hospitalization

Delirium etiology during index hospitalization will be determined using the **Delirium Etiology Checklist (Appendix T)** which classifies delirium etiologies into 13 categories.⁶⁰ Using medical record review, delirium etiology will be independently determined by two physician reviewers who have expertise in delirium; any disagreements will be adjudicated by a third physician reviewer. If the inter-rater reliability between the emergency physician and physician reviewers is good (kappa > 0.60), then the emergency physician's delirium etiology rating will be used for the LCA. For the purpose of our analysis, delirium etiologies will be collapsed into the following categories based upon our preliminary data: (1) CNS, (2) metabolic, (3) systemic infection, and (4) other. The physician reviewers will also record what treatments were provided and determine if the delirium etiologies were treated adequately.

Additional data will be collected from the medical record and is summarized in **Table 5**.

	Outcome Variable	Description	Source	Length
Primary Outcome	Repeatable Battery for the Assessment of Neuropsychological Status (RBANS, Appendix E) ⁶⁷	A neuropsychological battery for global cognition which evaluates immediate and delayed memory, attention, visuospatial construction, and language. It has been validated in subjects with mild cognitive impairment, moderate to severe traumatic brain injuries, vascular dementias, and Alzheimer's disease. ⁶⁷⁻⁷¹ Scores range from 40 to 160, and the population mean (SD) is 100 (15).	Patient	30 mins
Secondary Outcomes	Delis-Kaplan Executive Function System (D-KEFS) Proverbs subscale (conceptual flexibility, Appendix F), the DKEFS Color Word Interference (inhibition, Appendix G), and DKEFS Verbal Fluency Category Switching subscale (monitoring, Appendix H) ⁷²	This neuropsychological battery will be used to quantify executive function. It assesses conceptual flexibility, inhibition, and monitoring which are the cornerstones of executive function. ⁷² An executive function composite score will be calculated from these three DKEFS subscales.	Patient	10 mins
	Older American Resources and Services Activities of Daily Living Scale (OARS ADL, Appendix I) ⁵⁸	It is based upon 7 basic and 7 instrumental activities of daily living. Scores range from 0 (completely dependent) to 28 (completely independent).	Patient or informant	5 mins

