Propositional density	1
Other Baseline Covariates	
Sex	1
Race	1
Education	1
Pre-illness function (OARS ADL)	1
Severity of illness (APS)	1
Comorbidity Burden	1
Interactions (Maximum)	
ADRD* Cognitive intervention	1
Total Degrees of Freedom (df)	11

Table C8.1.a. Covariates and interaction terms for multivariable linear regression.

[figure not shown]

Figure C8.3.a. Three hypothetical latent classes or phenotypes for delirium.

(arousal, psychomotor, severity, etiology, and pathophysiology) and separate them into mutually exclusive classes. This technique can be used to obtain phenotypes of delirium and determine if these novel phenotypes are associated with 4-month global cognition. Based upon our preliminary study (**Section C1.5**), pre-existing ADRD may strongly influence these delirium latent classes and will be considered for the LCA. The “best” number of latent classes is usually determined a priori by the researcher and we hypothesize that the cohort will be represented by three delirium phenotypes (**Figure C8.3.a**): no or mild, moderate, or severe 4-month cognitive impairment. The sensitivity of this hypothesis, model fit, and identification of the correct number of unique delirium phenotypes will be evaluated by comparing the models assuming different number of classes using the bootstrapped likelihood ratio test, which is a parametric bootstrap method that uses bootstrap samples to estimate the distribution of the log likelihood difference test statistic.⁸⁷

Once the latent classes have been identified, we will explore if the delirium phenotypes identified by LCA modify the association between the cognitive training and rehabilitation intervention and 4-month global cognition using multivariable linear regression as described in **Section C8.1a** using the formula below:

$$\text{Aim #3 Formula} \quad \begin{array}{l} \text{4-month global cognition} = \end{array} \quad \begin{array}{l} \text{Cognitive training /} \\ \text{rehabilitation} \\ \text{intervention} \end{array} \quad + \quad \begin{array}{l} \text{Phenotypes identified} \\ \text{by latent class analysis} \end{array} \quad + \quad \begin{array}{l} \text{+ premorbid cognition + premorbid} \\ \text{intelligence + covariates +} \\ \text{cognitive intervention*phenotypes} \end{array}$$

The multivariable linear model for Aim #3 will be adjusted for the covariates listed **Table C8.1.a.**

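### Aim 3 enters two overlapping activity ratings as separate LCA indicators and names only the bootstrapped likelihood ratio test for class number, so at least moderate overlap between them can by itself support three classes

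*Protocol*

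**What the plan says.** Aim 3 (Protocol 2.0) is to "identify novel delirium phenotypes (latent classes) based on psychomotor activity, arousal, severity, etiology, and pathophysiological plasma biomarkers" and then to explore whether the classes modify the intervention effect. Protocol 9.3 lists the same five domains and adds that pre-existing ADRD will be considered for the analysis.

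Protocol 5.2.b codes arousal from the RASS as decreased, normal or increased. For the DMSS-4, "Patients will be categorized into hypoactive, hyperactive, mixed, and no psychomotor subtype delirium". Both come from the same contact: "arousal, psychomotor activity, and severity can be observed while performing the delirium assessments". Protocol 5.6 lists IL-6 and CRP as two markers of inflammation, with PAI-1 and S100B for the other pathways.

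On class number, Protocol 9.3 sets three as an a priori hypothesis and describes the three phenotypes by degree of cognitive impairment at four months. The hypothesis, the model fit and the class count "will be evaluated by comparing the models assuming different number of classes using the bootstrapped likelihood ratio test". The resulting classes then enter a regression of 4-month cognition with a phenotype-by-intervention interaction.

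Neither document mentions within-class independence, bivariate residuals, direct effects, an information criterion or class separation. SAP section 4 covers only the randomized comparison, so the SAP holds no Aim 3 analysis that would supply these.

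**The concern.** A standard latent class model explains every association between indicators by class membership. The bootstrapped test simulates its null from the fitted smaller model, which carries the same assumption. If two indicators remain associated because they rate much the same behaviour, the smaller model misfits, the test rejects it, and the result is read as another phenotype.

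RASS and DMSS-4 are a likely pair of this kind: one runs from sedation to agitation, the other from hypoactive to hyperactive, and the same staff observe both at one visit. IL-6 and CRP are a second plausible pair.

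The interpretation of Aim 3 is at stake. A finding of three classes could be taken as support for three novel phenotypes when it shows only that two activity ratings agree. The phenotype-by-treatment test could then largely repeat the arousal and psychomotor effect-modification analyses already in Protocol 9.1 and SAP 8.4 (items 5 and 6).

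**Working it through.** The plan gives no sample size, power or error rate for Aim 3, so there is no figure to reproduce. The check is whether the mechanism works at the trial's size.

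**Algebra.** RASS has 3 levels and DMSS-4 has 4. If class is set equal to RASS level, RASS is constant within class and so independent of DMSS-4. Any 3 × 4 table is thus reproduced exactly by at most three locally independent classes. Three, the hypothesised number, is also the number that overlap alone can produce.

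**Size of the signal.** Cramér's V satisfies X² = n × V² × min(3−1, 4−1) = 2nV². With n = 350 (Protocol 2.0):
- V = 0.2: 2 × 350 × 0.04 = 28
- V = 0.4: 2 × 350 × 0.16 = 112
- V = 0.6: 2 × 350 × 0.36 = 252
- V = 0.8: 2 × 350 × 0.64 = 448

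For scale, the simulated 95% cut-off for one versus two classes was 32.0 in a similar eight-indicator set-up at n = 282. An association of V = 0.2 is therefore near the cut-off, and V = 0.4 is far beyond it.

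**Simulation.**
- Inputs from the documents: RASS 3 levels, DMSS-4 4 levels, etiology 4 categories (Protocol 5.3), four biomarkers, N = 350.
- Assumptions: arousal decreased/normal/increased 50/35/15%; hypoactive/hyperactive/mixed/none 45/12/13/30%; severity in 3 levels, because a score of none should be rare in delirious patients; biomarkers binary; test level 0.05; pre-existing ADRD left out. RASS and DMSS-4 are associated with each other; everything else is independent.
- Method: EM fits with 12 random starts; sequential tests of 1 v 2, 2 v 3 and 3 v 4 classes; bootstrap null pooled over replicates; 120 replicates per scenario. Monte Carlo standard error √(p(1−p)/120), for example √(0.80 × 0.20/120) = 3.7 points.

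| V (assumed) | 1 class | 2 | 3 | 4 | BIC selects 3 |
|---|---|---|---|---|---|
| 0 | 96% | 4% | 0% | 0% | 0% |
| 0.2 | 54% | 38% | 8% | 1% | 0% |
| 0.4 | 0% | 16% | 80% | 4% | 0% |
| 0.6 | 0% | 0% | 95% | 5% | 59% |
| 0.8 | 0% | 0% | 92% | 8% | 100% |

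Rows may not add to 100% because of rounding. With no overlap the test keeps its nominal error. At V = 0.2 one class is rejected in 46% of datasets.

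**Sample size.** The documents give enrolment as 350, 500 (Protocol 11.0) and 282 (SAP 8.7). At V = 0.6 the test selects three classes in 96% at both 282 and 500, so the result does not turn on which figure applies.

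**Replication.** A separate simulation at N = 350 selected three classes in 0/40 datasets at V = 0, 1/30 at 0.20, 19/30 at 0.37 and 29/30 at 0.57.

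**BIC.** Here each extra class adds 14 item probabilities and 1 class weight, a penalty of 15 × ln 350 = 88. Two extra classes cost 176. A signal of 112 (V = 0.4) cannot pay for that, while 252 (V = 0.6) can, which agrees with 0% and 59%. At V = 0.6 BIC selects three classes in 14% at N = 282 and 95% at N = 500. A second criterion helps but does not remove the problem under strong overlap.

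**Removing the overlap.** With the two ratings merged into one indicator (V = 0.6, N = 350), the test selects one class in 93%, two in 7% and three in 0%.

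**The case against.** The strongest reply is that association between indicators is exactly what latent class analysis uses. The simulated data can be written as a three-class model, so the test is detecting something real, and whether an arousal/motor cluster deserves the name phenotype is a matter of interpretation. This stands as far as it goes. It also states the difficulty: the test alone cannot tell a class that spans severity, etiology and biomarkers from agreement between two ratings.

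A reader might go further and infer that Aim 3 is bound to confirm three phenotypes when none exists. The documents do not support that:
- They give no RASS/DMSS-4 association, and at V = 0.2 three classes appear in only 8% of datasets.
- Three is an a priori hypothesis that the test checks, and it is tied to 4-month impairment. Activity-only classes would match the number but need not track impairment, which Protocol 9.3 also plans to examine.

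Nor is it shown that the phenotype test would be a hypoactive-versus-other comparison under another name. In a simulation at N = 282, class membership had median V of 0.74 to 0.84 with RASS and DMSS-4 and 0.16 or less with the other indicators, but that was for two classes; no such profile is available for three. Because arousal and psychomotor modification are tested separately, a comparison of results could also reveal redundancy.

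The simulations simplify the plan: severity was collapsed, ADRD omitted, biomarker coding assumed and the bootstrap null pooled. Independence of all other indicators is a worst case. The IL-6/CRP pair was not simulated, so for that pair the concern rests on the same reasoning without a figure.

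**Conclusion.** The concern holds as a possibility that the plan leaves unchecked. If RASS and DMSS-4 overlap at least moderately (V of about 0.4 or more, an assumption), the one named test can support three classes with no structure in severity, etiology or biomarkers: 80% of datasets at V = 0.4 and 92 to 95% at V = 0.6 to 0.8. With weak overlap three classes are rare, though rejection of a single class is already far above 5%.

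Classes that arise this way would mainly reflect activity level, since in these simulations nothing else carries association. The consequence is confined to Aim 3, whose effect-modification step is exploratory. The primary analysis and the SAP's other analyses do not use the classes. The change is worth making because it is cheap and decides what a three-class result can be said to mean.

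**What to change.** In Protocol 9.3, or in a separate analysis plan for Aim 3:

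1. Keep the indicators as Aim 3 names them.
2. Before accepting an extra class, inspect the bivariate residuals of the smaller model.
3. Where RASS and DMSS-4, or IL-6 and CRP, show residual dependence, refit with a direct effect between them. Use a single combined activity indicator as a sensitivity analysis. It need not be the main analysis, because merging two factors that Aim 3 lists separately is a debatable choice.
4. Base the class number on the bootstrapped test after those effects are allowed, with BIC reported beside it.
5. Report how well the classes separate on severity, etiology and biomarkers, so that a reader can see whether they are more than activity groups.

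Only the combined indicator was simulated; the direct-effect model addresses the same dependence but has no error rate here. The cost is some plan wording and a little more analysis work, with no new data and no added patient burden. The downside is that fewer or less distinct phenotypes may be found.

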To account for **pre-illness cognition**, we will obtain the **Quick Dementia Rating Scale (QDRS, Appendix K)** and **Everyday Cognition (eCOG, Appendix U)** scales from a qualified informant (caregiver, offspring, spouse, sibling, or having known the patient >5 years). A qualified informant is present in 97% of delirious ED patients. **Pre-existing ADRD** will be defined as a

QDRS > 5.0, ADRD documented in the medical record, or prescribed an acetylcholine esterase inhibitor (galantamine, donepezil, and rivastigmine) before randomization.

We will also account for ***pre-morbid intelligence***, which is considered a measure of cognitive reserve, by calculating ***propositional density*** using the patient's writing samples written prior to the acute illness. Propositional density is the number of propositions per 10 words, and its measurement early and late in life has been shown to be strongly associated with future dementia status.^{53,54} We will use the Computerized Propositional Idea Density Rater (CPIDR version 3.2, Athens, GA) to calculate propositional density automatically.^{55,56} While propositional density remains stable over time even in patients with dementia,⁵⁷ We will attempt to collect the earliest writing samples available. Based on our pilot study, approximately 90% of older ED patients with a qualified informant will have writing samples available for analysis.

5.2.d. Additional prospective data collected at enrollment.

To ascertain ***pre-illness function***, we will collect the ***Older American Resources and Services Activities of Daily Living (OARS ADL, 2 min, Appendix L)*** at enrollment from the patient or qualified informant.⁵⁸ Scores range from 0 (completely dependent) to 28 (completely independent). ***Nutritional status*** will be determined by the ***Mini-Nutritional Assessment (MNA, Appendix M)***.⁵⁹ The MNA ranges from 0 (malnourished) to 14 (normal nutritional status). We will also determine ***pre-illness frailty*** using the ***Clinical Frailty Scale (Observational, Appendix N)*** which is based upon comorbidities, functional status, and cognition. This scale ranges from 0 (no frailty) to 9 (terminally ill). ***Patient demographics***, including age, race, sex, marital status, years of education, highest occupation, weight, height, and place of residence will be recorded. Hospitalization within 6 months, substance abuse history, and hearing or visual impairment will also be obtained.

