Secondary analyses will also be performed. We will perform a per protocol analyses; for the multivariable linear regression model, the dose of the interventions (total duration of cognitive training and total duration of cognitive rehabilitation) will be the primary independent variables instead of treatment assignment (cognitive training/rehabilitation versus placebo). We will determine if early cognitive training and rehabilitation are associated with our 4-month secondary endpoints such as the individual RBANS cognitive domains (immediate and delayed memory, attention, language, and visuospatial construction), executive function, functional status, rehospitalization, nursing home placement, and death. We will also determine if early cognitive training reduces delirium duration, hospital length of stay, and discharge to a post-acute care facility. We will also explore if there are specific interventions that potentiate the cognitive intervention's effect such as time-to-cognitive training, discharge to a post-acute care facility, and physical activity during cognitive rehabilitation (mean Life Space questionnaire scores). We will explore if these factors modify the association between the cognitive intervention and 4-month global cognition.

9.2. Data analysis for Aim #2 (fMRI). To test if frontoparietal network connectivity, as characterized by BOLD fMRI, improves with cognitive training/rehabilitation compared with controls, we will apply the co-registered z-statistic maps in a mixed effects model to evaluate regions that differ in activation between the two groups, after separately modeling age, sex, and pre-illness QDRS. Group-level z-statistics and corrected p-values will be reported. As a supplementary analysis, we will also explore whether (i) regional tissue volumes at the imaging MRI time point vary between groups and (ii) cortical perfusion quantified from pCASL varies between groups. For these comparisons, a Wilcoxon rank-sum test or Student's t-test will be applied. With a sample size of 50 (25 per group), we will have sufficient power to detect a 30% improvement in frontoparietal cortex network connectivity with 80% power and a two-sided alpha of 0.05.

9.3. Data Analysis for Aim #3 (identify novel delirium phenotypes using LCA): Aim #3 will use LCA to identify hidden groups based on the observed delirium subtypes

	df
Primary Independent	
Cognitive intervention	1
Pre-illness Cognition / Intelligence	
Pre-illness ADRD	1
Pre-illness QDRS	1

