8.1. Descriptive Analysis

To characterize the study sample, demographic, clinical, and lab data will be described overall and by treatment arm. Categorical variables will be described using frequencies and proportions; continuous variables will be described using means and standard deviations as well

as medians and interquartile ranges (IQR) when appropriate. For the proportional odds logistic and logistic regression models, odds ratios (OR) with their 95% confidence intervals (95%CI) will be presented.

8.2. Primary outcome analysis:

Our primary analysis will be an intention-to-treat comparison of 4-month global cognition between those who receive and do not receive the cognitive training and rehabilitation intervention. The association of 4-month global cognition with the cognitive intervention vs usual care will be assessed using proportional odds logistic regression adjusting for a priori defined covariates as listed below in order of priority depending on the degrees of freedom available for each outcome:

Priority	Variable	Description
1	Pre-illness cognition	Quick Dementia Rating System is a 10-item questionnaire ranges from 0 to 30, with higher scores representing greater cognitive impairment. ^{40,41}
2	Pre-illness ADRD	Defined as a QDRS > 6, ⁴⁰⁻⁴² past history of ADRD in the electronic health record, or prescribed a home acetylcholine esterase inhibitor (i.e., donepezil) with ≥ 1 ADL impairment in the pre-illness OARS ADL. ⁴³
3	Age	Age in years at the time of enrollment
4	Pre-illness function	Older American Resources and Services Activities of Daily Living (OARS ADL) scale which assesses 7 basic and 7 instrument ADLs. ²⁹
5	Severity of illness	Acute Physiology Score of the Acute Physiology and Chronic Health Evaluation II (APACHE II) which is based on 12 laboratory, vital sign, and GCS. ⁴⁴
6	Comorbidity burden	Elixhauser comorbidity burden based on 31 comorbid conditions ⁴⁵
7	ADRD*treatment assignment interaction	To determine if cognitive intervention
8	Pre-illness Frailty	Clinical Frailty Scale (CFS) range from 0 (no frailty) to 9 (terminally ill) and is based on patient's comorbidities, and baseline cognition and function. ^{35,46}
9	Years of education	
10	Central nervous system etiology	Determined by 2 expert physician raters. Any disagreement was adjudicated by a third expert physician rater.
11	Race (Black vs non-Black)	
12	Sex	

Table 4. Covariates considered for the multivariable regression models in order of importance.

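### The exploratory Aim 3 model takes its covariates from a table without age, so phenotype differences in 4-month RBANS may partly reflect age (minor)

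*Protocol*

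**What the plan says.** Protocol 9.3 gives two uses for the latent classes. One is to "determine if these novel phenotypes are associated with 4-month global cognition". The other is to "explore if the delirium phenotypes identified by LCA modify the association between the cognitive training and rehabilitation intervention and 4-month global cognition". The model is a linear regression of 4-month global cognition on intervention, phenotype, premorbid cognition and intelligence, covariates, and intervention-by-phenotype. On the covariates it says: "The multivariable linear model for Aim #3 will be adjusted for the covariates listed" in Table C8.1.a.

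That table, captioned "Covariates and interaction terms for multivariable linear regression", lists:
- the intervention;
- pre-illness ADRD, QDRS and propositional density;
- sex, race, education, OARS ADL, APS and comorbidity;
- ADRD-by-intervention.

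Age is absent.

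Elsewhere age is treated as relevant. SAP 8.2, Table 4, gives it priority 3 ("Age in years at the time of enrollment") for 4-month RBANS, above function, severity, comorbidity, education, race and sex. SAP 8.4 names it first among the candidate effect modifiers. Protocol 9.2 fits the imaging model "after separately modeling age, sex, and pre-illness QDRS". Protocol 5.2.d records demographics at enrolment, "including age, race, sex, marital status, years of education" among them.

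SAP section 4 states one objective, which corresponds to protocol Aim 1. The SAP contains no latent class analysis.

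**The concern.** Protocol 9.1 and 9.3 share Table C8.1.a. The SAP replaced that list for Aim 1 and brought age in, but nothing did the same for Aim 3.

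The gap matters more in Aim 3 than it would in a randomised comparison. Treatment arms are balanced on age in expectation, but latent classes are not. They are built from arousal, psychomotor activity, severity, etiology and biomarkers, and the protocol itself expects pre-existing ADRD to shape them strongly. Classes that differ on ADRD may well differ on age. A phenotype could then appear to carry worse 4-month cognition partly because its members are older. The model would also leave in the residual some variance that a recorded baseline value could remove.

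**Working it through.** **1. Is there room for an unlisted age term?** Intervention 1 + (ADRD, QDRS, propositional density) 3 + (sex, race, education, OARS ADL, APS, comorbidity) 6 + ADRD-by-intervention 1 = 11. This equals the table's stated total, so no hidden age term exists. Age does not enter through APS either: protocol Table 5 describes it as 12 physiologic and laboratory measurements.

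**2. The plan's own sample size.** SAP 8.7 uses SD 12.4, difference 6.0, two-sided alpha 0.05, 80% power and 1:2 allocation. A t-based calculation gives 50.9 and 101.9, so 51 + 102 = 153, as stated. Enrolment: 51/(0.70 × 0.78) = 93.4, rounded up to 94, and 94 × 3 = 282, as stated. These are Aim 1 figures. No sample size is given for the Aim 3 analysis, so 153 is used below only as a working number of completers.

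**3. Shift in the phenotype main effect.** Shift = age slope × mean age gap between classes. Both inputs are assumptions.

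| Slope (points/year) | Gap 2 years | Gap 4 years | Gap 6 years |
|---|---|---|---|
| 0.1 | 0.2 | 0.4 | 0.6 |
| 0.25 | 0.5 | 1.0 | 1.5 |
| 0.5 | 1.0 | 2.0 | 3.0 |

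Against the SAP's 6.0-point threshold, used here only as a yardstick, this is 3% (0.2/6.0) to 50% (3.0/6.0).

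**4. Precision.** Inflation of the standard error when age is omitted = 1/√(1 − partial R²). For an assumed partial R² of 0.02, 0.05 and 0.10 this is 1.010, 1.026 and 1.054, or about 1% to 5%.

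**5. Simulation.** 3,000 replicates with N = 153, one third treated, three equally likely classes whose mean ages step by 3 years (6 between extremes), within-class age SD 7 and residual SD 12. There was no true phenotype effect and no true phenotype-by-intervention effect.

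*Age prognostic only:*

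| Slope | Main effect, no age | Main effect, with age | Interaction, no age / with age | SE of interaction, no age / with age |
|---|---|---|---|---|
| −0.1 | −0.52 | 0.09 | −0.06 / −0.06 | 5.13 / 5.14 |
| −0.25 | −1.49 | 0.04 | −0.03 / −0.04 | 5.21 / 5.17 |
| −0.5 | −2.95 | 0.05 | −0.12 / −0.10 | 5.35 / 5.16 |

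The main effect (extreme classes) absorbs age when age is omitted and returns to about zero when it is added. The interaction is centred near zero either way.

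*Age also modifying treatment by 0.25 points per year:* the apparent phenotype interaction was 1.45, 1.36 and 1.69 without age, and 1.47, 1.38 and 1.69 with an age main effect. The expected value is 6 × 0.25 = 1.5. An age main effect does nothing here.

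**6. Degrees of freedom with three classes.** Following the Aim 3 formula: intervention 1 + phenotype 2 + 3 + 6 + intervention-by-phenotype 2 = 14, or 15 with age. 153/15 = 10.2 patients per df. Keeping ADRD-by-intervention as well gives 16, and 153/16 = 9.6. SAP 8.2 allows one df per 10 to 15 completers, which is 10 to 15 df at 153.

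**The case against.** Five points on the other side have weight.

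- *The interaction is protected.* A reader might infer that leaving out age biases the phenotype-by-intervention test. Randomisation prevents that when age is only prognostic, and step 5 agrees. If age modifies the treatment effect, a phenotype interaction can reflect age, but an age main effect would not remove it. This stands, and it confines the case for an age covariate to the main effect and a little precision.
- *The size rests on assumptions.* The documents give no age slope, no age gap and no partial R² beyond QDRS, ADRD, OARS ADL and comorbidity. Protocol Table 6 gives a population mean of 100 and SD of 15 for the RBANS without saying whether the norms are age-specific; if they are, the residual slope would be smaller. This stands too, although the SAP still ranks age third for this score.
- *Aim 3 is not the odd one out in the protocol.* Protocol 9.1 uses the same table. The difference arose only when the SAP revised Aim 1. Aim 2 has an imaging outcome and lends weak support. The gap is best read as a cross-reference left behind, and not as a contradiction about one analysis.
- *Aim 3 speaks of association and is exploratory.* The effect-modification part is explicitly exploratory, and the randomised comparison already has age under the SAP. This supports a low severity.
- *The df are tight.* The 15-df model meets only the lenient end of a SAP rule that was not written for Aim 3, and only if ADRD-by-intervention is dropped. This is a real trade-off that should be stated.

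**Conclusion.** The omission is real: the Aim 3 model is tied to a table without age, and nothing in the SAP changes that. The consequence is conditional. If the classes differ in age, and age predicts RBANS beyond the cognition and function terms already included, the phenotype main effect will partly reflect age, by 0.2 to 3.0 points over the assumed ranges. The precision loss is about 1% to 5% in standard error for an assumed partial R² of 2% to 10%.

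The documents do not support saying that phenotype differences will carry age differences, that the phenotype-by-intervention result is biased by a prognostic age effect, or that the primary comparison is affected. The point is minor, and worth acting on because age is already collected and the change is cheap.

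**What to change.** Before the phenotype models are run:

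1. Add age at enrolment to the covariates for the Aim 3 model.
2. State that intervention-by-phenotype is carried, as the Aim 3 formula shows, in place of ADRD-by-intervention. Give the resulting count: 15 df with three classes. If ADRD-by-intervention is kept, acknowledge 16 df.
3. Add age-by-intervention as a sensitivity analysis, since this is what addresses whether an apparent phenotype interaction reflects age as an effect modifier.

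The cost is a line or two of text and one df in the main Aim 3 model. The sensitivity model uses one more, 16 in all, or 9.6 completers per df at 153. That is just outside the SAP's rule and is a reason to keep it secondary. No new data are needed.
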